13.5. Safety Analyses

The type, severity, duration and frequency of reported ocular adverse events will be tabulated. Adverse events will also be summarized for events that were considered treatment-related.

14. GCP, ICH and ETHICAL CONSIDERATIONS

This study will be conducted in compliance with Good Clinical Practices (GCPs), including International Harmonization (ICH) Guidelines, and in general, consistent with the 1996 version of the Declaration of Helsinki. In addition, all applicable local, state and federal requirements will be adhered to.

This study is to be conducted in accordance with Institutional Review Board regulations. The investigator will obtain appropriate IRB/ethics committee approval prior to initiating the study.

The study will be registered with clinicaltrials.gov.

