9.2.1. Preoperative

At the preoperative exam, subjects will be consented, qualified for the study (compared with inclusion/exclusion criteria), and assigned a study ID/subject number. Subject numbers will be assigned sequentially at each site in the order of enrollment. Pre-operative qualification should take place no more than 60 days prior to surgery.

A medical history will be taken and exams will include the tests described below:

- manifest refraction,
- visual acuity

In addition, all site-specific, routine, usual standard of care preoperative measures should be undertaken. Data obtained from examinations within 24 months of consent are acceptable.

Measurements should be made as described in section 9.3 below.

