9.5. Discontinued Subjects

Discontinued subjects are those who do not have an exit visit or who come into the office to be exited prior to the scheduled final study visit. Subjects may be discontinued from the study at any time if, in the opinion of the investigator, their continued participation in the study poses a risk to their health. The reasons for discontinuation include:

- a. Adverse event;
- b. Lost to follow-up;
- c. Subject decision unrelated to an adverse event;
- d. Protocol violation;
- e. Treatment failure;
- f. Other.

To ensure the safety of all subjects who discontinue prior to Visit 6, investigators should assess each subject and, if necessary, advise them of any therapies and/or medical procedures that might be needed to maintain their health. Any changes in medical health and/or use of concomitant medications should also be captured.

10. ANALYSIS PLAN***10.1. Analysis Data Sets***

All subjects who are enrolled in the study will be evaluated for safety. Efficacy analyses will be performed based on data from those eyes where uncomplicated cataract surgery with Vivity IOL implantation was completed.

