13.1. General Information

An Adverse Event (AE) is any untoward medical occurrence in a subject who is administered a study treatment regardless of whether or not the event has a causal relationship with the treatment. An AE, therefore, can be any unfavorable or unintended sign (including an abnormal laboratory finding), symptom, or disease temporally associated with the study treatment, whether or not related to the treatment. In clinical studies, an AE can include an untoward medical occurrence occurring at any time, including run-in or washout periods, even if no study treatment has been administered.

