13.3. Procedures for Recording and Reporting AEs and SAEs

Subsequent to signing an informed consent form, all untoward medical occurrences that occur during the course of the study must be documented on an Adverse Event Form (AEF). A separate AEF must be filled out for each event. When possible, signs and symptoms indicating a common underlying pathology should be documented as one comprehensive event. For each recorded event, the AE documentation must include the onset date, outcome, resolution date (if event is resolved), intensity (i.e., severity), any action with study treatment taken as a result of the event, and an assessment of the adverse event's relationship to the study treatment.

Nonserious Adverse Events

A nonserious AE is defined as any untoward change in a subject's medical health that does not meet serious criteria noted below (e.g., is not life-threatening, does not require hospitalization, does not prolong a current hospitalization, is not disabling, etc.). All adverse events must be reported regardless of whether or not they are related to the study treatment.

For nonserious adverse events, an AEF containing all available information will be collected on a routine basis and submitted to the Medical Monitor at the close of the study.

Serious Adverse Events

A serious adverse event (SAE) is defined as any adverse experience that meets any of the following criteria:

- Results in death.
- Is life-threatening.

NOTE: Life-threatening means that the subject was at immediate risk of death from the reaction as it occurred; i.e., it does not include a reaction which hypothetically might have caused death had it occurred in a more severe form.

- Requires inpatient hospitalization or prolongation of existing hospitalization.

NOTE: In general, hospitalization signifies that the individual remained at the hospital or emergency ward for observation and/or treatment (usually involving an overnight stay) that would not have been appropriate in the physician's office or an out-patient setting. Complications that occur during hospitalization are AEs. If a complication prolongs hospitalization or fulfills any other serious criteria, the event is serious. When in doubt as to whether "hospitalization" occurred, the event should be considered serious.

- Results in persistent or significant disability/incapacity. Disability is defined as a substantial disruption of a person's ability to conduct normal life functions.

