18.2. Patient Discontinuation

Each study patient may voluntarily discontinue the study at any time they choose. Study patients who cannot complete the study for administrative reasons (e.g., non-compliance, failure to meet visit schedule, etc.) will be discontinued from the study. Study patients discontinued during the enrollment phase (prior to surgery) of the study will be replaced.

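### Section 13.5 plans no table for non-ocular adverse events judged Not Related, even serious ones, and fixes no denominator for adverse event frequencies

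*Combined protocol and SAP*

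**What the plan says.** **Collection.** Section 13.3 starts recording at signed consent, asks for a separate form for each event, and states: "All adverse events must be reported regardless of whether or not they are related to the study treatment". It also requires every serious event, related or unrelated, to go on a dedicated form. The definition in 13.1 reaches events that occur "even if no study treatment has been administered".

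**Tabulation.** Section 13.5 has two sentences: "The type, severity, duration and frequency of reported ocular adverse events will be tabulated" and "Adverse events will also be summarized for events that were considered treatment-related". It plans no table of all adverse events and none of serious adverse events.

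**Who is counted.** Section 10.1 says: "All subjects who are enrolled in the study will be evaluated for safety". Section 9.2.1 places consent and numbering at the preoperative visit: "Subject numbers will be assigned sequentially at each site in the order of enrollment". Section 18.2 adds: "Study patients discontinued during the enrollment phase (prior to surgery) of the study will be replaced". Section 10.2 says that its general summaries cover the eyes that complete the study. Section 13.5 promises a frequency without saying of what: subjects or eyes, enrolled, operated or completing.

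**The concern.** The set of events collected is wider than the set tabulated, and the difference is decided by two labels: ocular or not, and related or not. For a non-ocular event, the causality call alone decides whether it reaches a table. That call is coarse. The causality subsection (numbered 12.3.1, within section 13) offers two categories, and Not Related includes events that are merely unlikely to be related. It asks about relation to the device, whereas 13.5 speaks of treatment. A non-ocular event put down to the surgery rather than the lens could thus be marked Not Related and drop out. The investigator and the Medical Monitor both assess causality, and 13.5 does not say whose assessment governs the summary.

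At stake is whether the safety results of a 20-subject study can be read as complete, and whether a percentage in them has one clear meaning.

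**Working it through.** **1. Which events reach a table.** Crossing the two labels used in 13.5, and reading its second sentence broadly so that it covers non-ocular events:

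| Event | Ocular tabulation | Treatment-related summary |
|---|---|---|
| Ocular, Related | yes | yes |
| Ocular, Not Related | yes | no |
| Non-ocular, Related | no | yes |
| Non-ocular, Not Related | no | no |

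The last row is empty even on the broad reading. Seriousness does not rescue it. The severity that 13.5 tabulates is the intensity scale of 12.3.1 (mild, moderate, severe), which is different from the seriousness criteria of 13.3. Section 10.2 does not fill the row either: it summarises measurements by time point for completing eyes and names no adverse event output.

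**2. The plan's own figure.** No safety rate or safety precision is stated. The only sizing figure, in section 11, is a half-width of 0.05 logMAR for a mean at n = 20 and SD 0.1. It reproduces: t(0.975, 19) × 0.1/√20 = 0.0468, which rounds to 0.05. It has no bearing on this point.

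**3. Effect of counting replaced subjects.** Inputs: 20 subjects and 40 eyes (7.1); safety evaluation of all enrolled (10.1); replacement before surgery (18.2). Let r be the number replaced who never had surgery. The documents give no value, so I assume 0 to 5, with 20 subjects operated on. With x subjects having an event, the rate is x/20 among those operated on and x/(20+r) among all enrolled. The ratio of the second to the first is 20/(20+r).

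| r | N | 20/(20+r) | One event | Two events |
|---|---|---|---|---|
| 0 | 20 | 1.000 | 5.0% | 10.0% |
| 1 | 21 | 0.952 | 4.8% | 9.5% |
| 2 | 22 | 0.909 | 4.5% | 9.1% |
| 3 | 23 | 0.870 | 4.3% | 8.7% |
| 5 | 25 | 0.800 | 4.0% | 8.0% |

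With no events, the exact two-sided 95% upper limit is 16.8% at N = 20 and 13.7% at N = 25.

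**4. Unit of analysis.** This needs no assumption about r. One ocular event is 1/20 = 5.0% of subjects or 1/40 = 2.5% of eyes, a twofold difference that 13.5 leaves open.

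**5. Monitoring of replaced subjects.** Table 15.1 marks adverse event monitoring only from the operative visit, while 13.3 records from consent. By that table, a subject lost before surgery could enter an all-enrolled denominator without any scheduled adverse event check.

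**The case against.** Four arguments weigh against the point.

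- **Nothing goes unreported.** A reader might infer that the events in the empty row are lost. The documents do not support that. Under 13.3 every event has a form, nonserious forms go to the Medical Monitor at study close, and serious events go to the Medical Monitor within one working day and to the IRB/IEC. This stands, and it confines the point to planned tables.
- **Causality is not a general filter.** Ocular events, those most relevant to an intraocular lens, are tabulated whatever their causality, and the Medical Monitor makes a second causality assessment. This also stands. It narrows the gap to non-ocular events but does not close it.
- **Dilution is not established.** A reader might infer that lens event rates are diluted. No section states a denominator of all enrolled subjects for event rates. Section 7.1 plans 20 enrolled, and 18.2 speaks of an enrollment phase before surgery, so the enrolled total could fairly be read as the 20 who reach surgery. Numbering at the preoperative visit points the other way, and 10.2 points to completing eyes. The text is ambiguous, so the direction of any error is not fixed, and at r = 0 there is no effect.
- **The shift is small, and an all-enrolled set has a rationale.** Exact 95% intervals are 0.1% to 24.9% for 1/20 and 0.1% to 21.9% for 1/23, and no safety test or threshold depends on a rate. An all-enrolled set also fits recording from consent. That justifies listing pre-surgery events for everyone enrolled. It does not make unoperated subjects a suitable denominator for lens event rates.

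**Conclusion.** The main point holds on the text alone and needs no assumption. A non-ocular adverse event judged Not Related is collected but enters no planned safety table, and this is equally true if it is serious. It is a restriction of tabulation, not of documentation or onward reporting.

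The denominator point is secondary and conditional. Rates could be diluted by 20/(20+r) only if replaced subjects count as enrolled and all enrolled subjects are used as the denominator. Over the assumed range of r from 0 to 5, the relative reduction runs from none to 20%. This supports reconciling 10.1, 10.2, 13.5 and 18.2. It does not support saying that the rates are diluted.

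The point is minor: it concerns the completeness and clarity of the safety results and leaves the primary visual acuity results untouched.

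**What to change.** **In 13.5:** tabulate all adverse events and, separately, all serious adverse events. Show ocular events per eye and per subject, and non-ocular events per subject, with the related subset inside each table. State whose causality assessment defines that subset, and whether it means related to the lens or to the study treatment more broadly.

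**In 10.1:** define the denominator for device and ocular event rates as the subjects, and the eyes, in which study surgery was started. List pre-surgery events separately for all enrolled subjects, including those replaced under 18.2. State that the completing-eyes rule in 10.2 does not apply to adverse events.

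**Cost:** a few sentences and one extra table in a 20-subject study, with no new data collection. The one downside is that rates may look slightly higher than they would with all enrolled subjects as the denominator.

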14.1 Confidentiality

The data collected will be data typical for the procedure(s) when performed on eyes outside the study. Any data collected will become part of the patient's clinical record. The data will be subject to the same privacy and confidentiality as other data in the clinical record.

Only the principal investigator, research consultant, and clinic staff will have access to the data collected. All data shared outside the practice will be de-identified; patients' protected health information will not be available and will not be reported in any analyses or publications. No data will be sold to third parties. De-identified (anonymized) data may be used for future research.

15. STANDARD EVALUATION PROCEDURES

Table 15.1. Proposed Visits and Study Assessments

(visits are by patient, with both eyes tested)

Activity	Pre-operative	Operative	Postoperative			
	Visit 1	Visit 2	Visit 3	Visit 4	Visit 5	Visit 6
			1 Day	1 Week	1 Month	3 Months
Informed Consent	X					
Demographics	X					
General Information: Medical History	X					
Surgery		X				
Manifest refraction	X			X	X	X
Monocular uncorrected distance VA	X		X	X	X	X
Monocular best corrected distance VA	X			X	X	X
Monocular uncorrected and best distance-corrected intermediate VA				X	X	X
Monocular uncorrected and best distance-corrected near VA				X	X	X
Binocular uncorrected and best-corrected distance VA						X
Binocular uncorrected and best distance-corrected intermediate VA						X
Binocular uncorrected and best distance-corrected near VA						X
Binocular distance corrected low contrast VA						X
IOLSAT Patient Satisfaction Survey						X
QUVID Visual Disturbance questionnaire						X
Monitor for Adverse Events and Device Deficiencies		X	X	X	X	X
Complete Exit Form ¹						X

¹ Complete Exit Form upon termination of subject participation, or at Visit 6, whichever occurs first.

* To be performed if deemed necessary by the investigator

16. CONFIDENTIALITY

No protected health information (PHI), including the patient's name and date of birth, will be collected; to ensure this, no PHI information is permitted to be entered on any of the Case Report Forms (CRFs). Subjects will only be identified by subject IDs and identities will be removed at the initial visit so that there is no further need to protect or destroy the information. Collected information will only be used for purposes of this

study and no information will be sold to third parties. The non-PHI information collected may be used for future research, though there is currently no plan to do so.

17. FINANCIAL AND INSURANCE INFORMATION/STUDY RELATED INJURIES

Every effort to prevent study-related injury will be taken by the Study Doctor and staff. In the event a patient is injured as a direct result of the study while following the Study Doctor's instructions and the study requirements, the patient will be instructed to contact his or her doctor immediately. The Study Doctor is to treat the injured subject as needed for those injuries caused directly by this research study. In the event of injury or illness caused by or occurring during a subject's participation in this research study, all charges for medical care provided to the subject will be billed to his or her insurance company. The Study Doctor or Sponsor does not offer to cover the medical care costs for injuries or illnesses that are not caused directly by the research study. The Sponsor does not offer to provide any other compensation, unless specifically agreed to elsewhere in this document. This information will be provided to each study subject before the start of the study in the consent form.

18. STUDY ENDPOINT CRITERIA

18.1. Patient Completion of Study

If a study patient has completed the final visit (Visit 6) of the study, he/she is considered to have completed the study.

18.2. Patient Discontinuation

Each study patient may voluntarily discontinue the study at any time they choose. Study patients who cannot complete the study for administrative reasons (e.g., non-compliance, failure to meet visit schedule, etc.) will be discontinued from the study. Study patients discontinued during the enrollment phase (prior to surgery) of the study will be replaced.

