10.2. Statistical Methodology

A summary of the data will be prepared for all measurement time points. Summaries of the changes observed between the 1 month and 3 month post-operative visits will also be summarized.

For variables measured on a continuous scale, these summaries will include the sample size, as well as the mean, standard deviation, median, minimum, and maximum. For variables measured on a categorical scale, summaries will provide the number and percentage of subjects who provided each score (or change in scores). These summaries will be provided for all eyes completing the study.

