11. SAMPLE SIZE JUSTIFICATION

The distribution of axial length ≥ 24.5 mm in the older population of is $\sim 17\%$.³ As a result, recruitment for qualifying candidates will be limited due to this natural population distribution. It is expected that 20 patients (40 eyes) will provide sufficient data to characterize the clinical performance of the lens. When the sample size is 20, a two-sided 95% confidence interval for a single mean will extend 0.05 from the observed mean, assuming that the standard deviation is known to be 0.1 logMAR and the confidence interval is based on the t-statistic.

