18.3. Patient Termination

A study patient will be terminated if the study patient develops any severe adverse event that may be related to the study. A study patient will receive appropriate treatment at the discretion of the investigator. Notification of termination will be clearly documented. These study patients are considered to have completed the study and will not be replaced.

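### Section 18.2 lets implanted subjects be discontinued for missed visits without a threshold, and Section 10.2 limits summaries to a loosely defined set of completers, so avoidable and possibly selective data loss is left open

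*Combined protocol and SAP*

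**What the plan says.** - **Discontinuation (18.2).** Subjects unable to finish for "administrative reasons (e.g., non-compliance, failure to meet visit schedule, etc.) will be discontinued from the study". The sentence is not limited to the period before surgery and does not say how many visits, or how late a visit, would count.
- **Replacement (18.2).** "Study patients discontinued during the enrollment phase (prior to surgery) of the study will be replaced". Nothing provides for replacing a subject lost after implantation.
- **Efficacy set (10.1).** "Efficacy analyses will be performed based on data from those eyes where uncomplicated cataract surgery with Vivity IOL implantation was completed". Completion of follow-up is not a condition.
- **Summaries (10.2).** They are planned for every measurement time point, but "These summaries will be provided for all eyes completing the study".
- **Completion (18.1 and 18.3).** Under 18.1, "If a study patient has completed the final visit (Visit 6) of the study, he/she is considered to have completed the study". Under 18.3, subjects terminated for a severe, possibly related adverse event also count: "These study patients are considered to have completed the study and will not be replaced".
- **Schedule (Table 15.1, 8.1, 9.3.3).** The primary outcome is binocular uncorrected acuity at three distances at 3 months. Table 15.1 schedules all binocular acuities, low-contrast acuity, IOLSAT and QUVID at Visit 6 only. Monocular acuity and refraction are also taken at 1 week and 1 month.
- **Window (Table 9.2-1).** Visit 6 is at 90 ± 20 days after the last eye's surgery. No rule covers a measurement outside that window.
- **Early exit (9.2.7).** Study examinations are to be done at premature exit if feasible. No text says whether those data are analysed.
- **Precision (11).** With 20 subjects the 95% interval "will extend 0.05 from the observed mean", taking the SD as 0.1 logMAR. There is no allowance for dropout.

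**The concern.** The lens stays in the eye whether or not a subject keeps to the visit calendar, so a 3-month acuity can often still be measured in someone who missed or delayed an earlier visit. A site that applies 18.2 to such a subject gives up the only scheduled measurement of the primary outcome and both questionnaires.

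Subjects who miss visits may see less well or be less satisfied than those who attend. They may also be simply busy, or content and seeing no need to return. If poorer outcomes are over-represented among leavers, the reported 3-month acuity and satisfaction look better than they should, and enrolling more subjects would not correct that. With 20 subjects, each is 5% of the sample.

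Section 10.2 adds a second problem. Read literally, it discards valid early measurements from anyone who later leaves. The analyst must also decide, possibly after seeing the data, whether the population is that of 10.1 or that of 10.2, and whether subjects terminated under 18.3 belong to it.

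**Working it through.** **1. The plan's precision figure.** Inputs from Section 11: n = 20, SD = 0.1 logMAR, two-sided 95%, t-statistic.

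Half-width = t(0.975, n−1) × SD / √n = 2.093 × 0.1 / √20 = 0.0468, which rounds to the stated 0.05. The figure reproduces with the subject as the unit; 40 eyes would give 0.0320.

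**2. Precision after losing implanted subjects.** Same formula, with fewer subjects:

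| Subjects measured | Half-width (logMAR) | To two decimals |
|---|---|---|
| 20 | 0.0468 | 0.05 |
| 19 | 0.0482 | 0.05 |
| 18 | 0.0497 | 0.05 |
| 17 | 0.0514 | 0.05 |
| 16 | 0.0533 | 0.05 |
| 15 | 0.0554 | 0.06 |

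Three losses widen the interval by about 10% (0.0514 / 0.0468 = 1.10). At the precision the plan uses, the stated figure changes only after five losses.

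**3. Possible bias.** If k of 20 subjects are missing and their mean is d logMAR worse than that of the observed subjects, the mean of all 20 is the observed mean plus (k/20) × d. The observed mean is therefore too favourable by (k/20) × d.

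The documents give neither k nor d. Taking k = 3 and d = 0.10 to 0.20 as assumptions:

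- d = 0.10: 3/20 × 0.10 = 0.015, and 0.015 / 0.0514 = 29% of the half-width at n=17.
- d = 0.20: 3/20 × 0.20 = 0.030, and 0.030 / 0.0514 = 58% of that half-width.

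**4. What each section costs a subject who leaves after implantation but before Visit 6.**

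| Data | Scheduled before Visit 6? | Effect |
|---|---|---|
| Binocular uncorrected acuity (primary) | No | Lost through 18.2; 10.2 makes no difference to scheduled data |
| IOLSAT, QUVID, binocular corrected and low-contrast acuity | No | Same |
| Monocular acuity and refraction at 1 week and 1 month | Yes | Observed if the visit took place, then dropped by 10.2 |

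**5. Who is a completer?** Under 18.1 it is a subject who had Visit 6. Under 18.3 it also includes a subject terminated for a severe, possibly related adverse event, who may never reach Visit 6. The 10.2 population therefore has two possible definitions, and neither equals the 10.1 set.

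**The case against.** The strongest reply is that 18.2 concerns subjects who are unable to finish. Read that way, it classifies people who have already dropped out and does not tell a site to remove a willing subject over one late visit. This largely stands: a reader might infer that any missed visit leads to removal, and the text does not say so. But failure to keep the schedule is one of its own examples and no threshold is given, so it does not prevent that use either.

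Second, the plan does seek data from leavers: 9.2.7 asks for examinations at premature exit, and the Visit 6 window already spans 40 days. That is a real mitigation. It is partial, because the examination is made at exit and not at 3 months, and 10.2 would leave the result out if the subject is not a completer.

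Third, 10.1 and 10.2 can be read together, with 10.1 setting eligibility and 10.2 a subset for summaries. That is possible, so they are better called unreconciled than contradictory. Which set governs the 3-month results still has to be stated.

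Fourth, correcting 10.2 might be thought to rescue the primary analysis. It would recover no scheduled primary data, since none is scheduled before Visit 6. Its benefit is to the early monocular and refractive summaries and to a clear population.

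**Conclusion.** The point holds as a gap in follow-up and population rules that should be closed; the study remains interpretable without the change. Section 18.2 permits avoidable loss of 3-month data in implanted subjects. Section 10.2 discards some observed early data and rests on an ambiguous definition of completion.

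Two stronger conclusions are not supported. A reader might infer that three losses break the promised precision. Unrounded, 0.0514 does exceed 0.05, but the plan's figure is itself 0.0468 rounded, and n=17 and n=16 round to the same value. A reader might also infer that the 3-month means will be biased. The documents give no dropout rate, and no size or direction of difference between leavers and stayers. The 0.015-0.030 logMAR (29-58% of the n=17 half-width) rests wholly on the assumption of three missing subjects who are 0.10-0.20 logMAR worse. It shows that selective loss of that size would matter more than the lost precision, not that it will occur.

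**What to change.** - **18.2.** State that non-compliance, or a missed or late visit, does not end data collection for an implanted subject who is willing to continue, and that a Visit 6 measurement is still sought. Voluntary withdrawal is unaffected.
- **10.2.** Replace the restriction to completing eyes with all observed data at each visit from the 10.1 set.
- **18.1 and 18.3.** Reconcile the two uses of completion with each other and with 10.2, so that it is clear how data from subjects terminated under 18.3 enter the summaries. This concerns the analysis label only, not when a subject should be terminated.
- **Out-of-window values.** Record the actual day of each 3-month measurement and report results both with and without values outside 70-110 days (90 ± 20). Which of the two is the main result is a matter of choice and should be fixed in advance.
- **Reporting.** Give the number of implanted subjects without 3-month data, with reasons.

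The cost is some rewording, one extra table, and a few 3-month values measured outside the window.
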